 - b) Urinary – urinary function including duration of post-op catheterization, mean UDI-6 scores⁴⁹, Hunskar Incontinence Severity Index, de novo voiding dysfunction rates, de novo incontinence rates
 - (i) Sexual – mean PISQ-IR⁵⁰ and specific rates of de novo dyspareunia
 - (ii) Bowel – bowel function using CRADI-8 scores⁴⁹
 - (iii) QOL – general SF-12 scores and sub-scales⁵¹, and Pelvic QOL mean PFIQ score⁴⁹; Functional Activity Assessment Scale⁴²

Secondary Aim 2 – Safety: These measures will require a statistical analysis plan and will be reported in the primary outcome manuscript.

- 1) Intraoperative safety – group comparisons of mean Operative time, estimated blood loss, blood transfusion, intra- and post-operative complications categorized using a modification of the Dindo Classification.⁵²
- 2) Adverse events – mesh related complications: mesh exposure in the vagina or mesh erosion into another organ and the classification of the intervention:
 - a) none or non-surgical medical intervention only

Confidential Please Do Not Copy

- b) minor or intra-office surgical intervention
- c) outpatient surgery
- d) inpatient surgery

Other complications possible in both arms:

- 1) Rates of pain captured from the modified Surgical Pain Scale⁴³, pain medication use, and location of pain with Pain Mapping Instrument
- 2) Pelvic infection:
 - a) perioperative infections
 - b) urinary tract infections
 - c) vaginal infections with flora uncommon to the vaginal canal
- 3) Vaginal shortening, de novo vaginal bleeding, atypical vaginal discharge, fistula formation, neuromuscular problems (including groin and leg pain)
- 4) Need for subsequent procedures – any surgical or non-surgical treatment for pelvic floor disorders (including urinary incontinence, voiding dysfunction, defecatory dysfunction or fecal incontinence, recurrent prolapse, and dyspareunia/pelvic pain). Any subsequent uterine or cervical office or Operating Room procedure in hysteropexy group (e.g., cervical biopsy, LEEP, hysteroscopy, D and C, hysterectomy).
- 5) Subsequent uterine or cervical pathology
- 6) Rates of vaginal scarring defined as de novo vaginal scar requiring medical or surgical intervention or adversely affecting quality of life
- 7) Rates of vaginal shortening, de novo dyspareunia, and worsening dyspareunia with AE survey instrument

Complication Monitoring

Groups will be compared for rates of “important complications”. The definition of “important complication” is:

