Perception of commercial bias: It is not unprecedented for a NIH-funded network to study a specific product (e.g., Botox, InterStim in the PFDN; Gynecare TVT, TVT-O and AMS Monarc in the UITN TOMUS study). If a non-commercial, home-made mesh bridge device was studied and proven inferior, proponents could argue it was the fault of a non-standardized device. For this reason, we favor a hysteropexy kit that lends itself to standardization. It is likely that industry funding will be available for this study, but industry will not participate in data collection, data analysis, or manuscript preparation.

P.2 Informed Consent

Patients who are candidates for study participation will be approached for enrollment. Written informed consent will be obtained in accordance with Institutional Review Board guidelines.

A common template for informed consent will be used by all centers, with modifications allowed to meet the necessary requirements of their respective institutional human subjects committees.

Uterovaginal Prolapse: Eligible women will be informed that traditional treatment for uterine prolapse includes hysterectomy with native tissue suture support; but more recently an option is uterine sparing with a mesh graft suspension and we do not know which procedure is more successful or more durable. Advantages of hysterectomy include eliminating the possibility of future uterine or cervical pathology while the disadvantages are the removal of a normal organ, possible earlier menopause, and the risks of intra-peritoneal injury, intra-abdominal bleeding and vaginal shortening. The advantage of the hysteropexy procedure includes preservation of a normal organ, normal timing of menopause, and decreased risk of intra-peritoneal complications. The disadvantages include possible future uterine or cervical pathology requiring additional surgery. All patients will be made aware of the risks of transvaginal mesh included in the FDA warning (e.g. mesh erosion, pelvic pain, and dyspareunia) via the study informed consent statement.

P.3 Data and Safety Monitoring Board

The NICHD has established a Data Safety Monitoring Board (DSMB) to oversee this study. Members of the DSMB are independent of the study investigators and include representatives with urology, urogynecology, and biostatistics expertise and a lay member. The DSMB will have regularly scheduled meetings, either in person or by teleconference. The Chair may request to meet more frequently.

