 - e. Sexual functional measures obtained at 6-month post-operative time points including:
 - i. PISQ-IR scale measures
 - ii. Risk of de novo dyspareunia
 - f. Bowel function obtained at 6-month post-operative time points using CRADI-8 scores

- g. Quality of Life (QO)L measures obtained at 6-month post-operative time points including:
 - i. General SF-12 physical component and mental component scales
 - ii. Pelvic QOL as measured by PFIQ total score and three subscales
 - iii. Functional activity as measured by the Activity Assessment Scale
- 3. Safety and tolerability of the two treatment regimens:
 - a. Intraoperative safety measured in each of the treatment arms including:
 - i. Operative time
 - ii. Estimated blood loss
 - iii. Proportion of participants with blood transfusion
 - iv. Intra- and post-operative complications categorized using a modification of the Dindo Classification.
 - b. Risk of adverse events on the two treatment arms as measured by proportion of participants with any of the following events:
 - Mesh related complications: mesh exposure in the vagina or mesh erosion into another organ; note that level of complication will be characterized into based on the following response classification schema: (a) None or nonsurgical medical intervention only; (b) Minor or intra-office surgical intervention; (c) Outpatient surgery; (d) Inpatient surgery
 - ii. Rates of pain captured from the modified Surgical Pain Scale, pain medication use, and location of pain with Pain Mapping Instrument.
 - iii. Pelvic infection
 - iv. Risk of perioperative infections
 - v. Risk of urinary tract infections
 - vi. Vaginal infections with flora uncommon to the vaginal canal
 - vii. Risk of any of De novo vaginal bleeding, atypical vaginal discharge, fistula formation, neuromuscular problems (including groin and leg pain)
 - viii. Need for subsequent procedures- Any surgical or non-surgical treatment for pelvic floor disorders (including urinary incontinence, voiding dysfunction, defecatory dysfunction or fecal incontinence, recurrent prolapse, and dyspareunia/pelvic pain). Any subsequent uterine or cervical office or Operating Room procedure in hysteropexy group (e.g., cervical biopsy, LEEP, hysteroscopy, D and C, hysterectomy).
 - ix. Subsequent uterine or cervical pathology
 - x. Risk of vaginal scarring defined as: De novo vaginal scar requiring medical or surgical intervention, or adversely affecting quality of life.

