10.2 Adverse Events

As described in Section 3.2, four types of measures will be utilized to characterize participant safety and tolerability measures. First, as a part of the inter-operative and peri-operative data collection forms, information will be collected on surgical complications that characterize the risk and tolerability of the procedure itself. Second, participants will be asked about specific targeted complications on both the post-operative visit and a standard study evaluation collected at 6-month intervals (with those complications automatically populating the AE form. Third, participants will be asked through a response to open-ended questions to report any post-surgery adverse events to the study coordinator or physician at the 6-week visit and at the subsequent follow-up visits at 6-month intervals. If a serious adverse event, particularly a hospitalization, occurs, the participants will be asked to report that immediately to the study coordinator or physician. All adverse events are captured by the study coordinator on the adverse event logs. Finally, specific pain information is being collected as a part of all follow-up visits to characterize differences in post-operative pain beyond 6 weeks.

The group of measures collected inter-operatively and peri-operatively includes those in the table below. These measures include continuous measures as well binary and ordinal measures. For the

continuous measures, summaries will be presented by treatment arm that include mean levels and standard deviations and linear models with treatment as the primary predictor, controlling for site will be used to test for differences by treatment arm. For the binary and ordinal measures, summaries will included counts and percentages associated with each level of the binary or ordinal measure and Cochran-Mantel-Haenszel statistics and associated p-value with analyses stratified by site will be used to characterize differences in the treatment arms.

The AEs collected through the standard AE form will be summarized using standard contingency tables by treatment arm. These summaries will be provided by individual treatment-emergent AEs, AEs by body system, and AEs by subject. In addition to these general descriptions, specific comparison of risk and differences across the treatment arms will be evaluated for the outcomes listed in the table below.

Summary of Safety V	ariables				
Inter-operative and peri-operative measures					
Variable	Туре	Definition			

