De novo vaginal bleeding	Binary	Based on masked data review this event was modified from De novo vaginal bleeding to any incident of vaginal bleeding because of the small number of events. It will be captured as a Yes response (AE or SAE) to Question 17 on the 6- to 60- Month Study follow-up form or by an event classified as a vaginal bleeding based on either the preferred term or comments for an event on the AE form.		
Atypical vaginal discharge	Binary	Atypical vaginal discharge will be captured as a Yes response (AE or SAE) to Question 16 on the 6- to 60- Month Study follow-up form or by an event classified as atypical vaginal discharge based on either the preferred term or comments for an event on the AE form.		
Fistula formation	Binary	Fistula formation will be captured as a Yes response (AE or SAE) to Question 16 of the Hospitalization form, Question 8 of the Post-operative visit form, or Question 7 or the 6- to 60- Month Study follow-up form or by an event classified as a fistula based on either the preferred term or comments for an event on the AE form		
Neuromuscular problems	Binary	A neuromuscular problem will be captured as a Yes response (AE or SAE) to Question 12 of the Hospitalization form, Question 14 of the Post-operative visit form, or Question 13 or the 6- to 60- Month Study follow-up form or by an event classified as a neuromuscular disorder based on either the preferred term or comments for an event on the AE form		
Need for subsequent procedures	Binary	Need for subsequent procedures will be classified as Yes if the responses on Section E of the Post-operative visit form or Section D of the 6-to-60 Month Evaluation form indicated that the participant had a procedure performed in		

		the office in response to a complication from the surgery or the participant had a reoperation operating room for complication related to surgery, recurrent POP, SUI, or any gynecologic, vaginal, pelvic, or reproductive organ condition.
Uterine or cervical pathology	Binary	Classified as Yes based on masked review of AE preferred terms.
Vaginal scaring	Binary	Vaginal scarring will be determined by an event classified as a vaginal scarring based on either the preferred term or comments for an event on the AE form.

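### SAP 10.2 does not implement the need-for-subsequent-procedures outcome that Protocol M.2 and SAP 3.2 define: non-surgical treatment and some office uterine or cervical procedures drop out

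*SAP*

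**What the plan says.** Protocol M.2, Secondary Aim 2, item 4 gives the outcome two parts. The first applies to either arm: "any surgical or non-surgical treatment for pelvic floor disorders (including urinary incontinence, voiding dysfunction", followed by other named disorders. The second belongs to one arm: "Any subsequent uterine or cervical office or Operating Room procedure in hysteropexy group (e.g., cervical biopsy, LEEP, hysteroscopy, D and C, hysterectomy". SAP 3.2, item 3b viii repeats both parts, the first beginning "Any surgical or non-surgical treatment for pelvic floor disorders".

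The Summary of Safety Variables table in SAP 10.2 then defines the variable to be coded. It takes responses from Section E of the post-operative visit form and Section D of the 6-to-60-month form. It is Yes if a procedure was performed in "the office in response to a complication from the surgery or the participant had a reoperation operating room for complication related to surgery", and the list of reasons for reoperation continues with "recurrent POP, SUI, or any gynecologic, vaginal, pelvic, or reproductive organ condition". The text before the table makes this the compared variable: "specific comparison of risk and differences across the treatment arms will be evaluated for the outcomes listed in the table below".

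SAP section 14, reserved for changes from the protocol, is still to be completed.

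**The concern.** The SAP contains two definitions of one outcome, and the one that drives the arm comparison is not the one the protocol planned. Analysts following 3.2 and 10.2 would report different counts from the same women.

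The outcome has weight. Need for subsequent procedures is named in Secondary Aim 2. The protocol sends these safety measures to the primary manuscript, and SAP section 2 says results go to the manufacturer for a report required by the FDA. One omitted component also bears on a harm that Protocol P.2 puts to women considering hysteropexy: "The disadvantages include possible future uterine or cervical pathology requiring additional surgery". Office procedures on a retained uterus or cervix are part of that burden, and the protocol asked for them to be counted.

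**Working it through.** The plan states no rate, power or alpha for this outcome, so there is no figure to reproduce. The check is a clause-by-clause comparison, then an illustration of direction.

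**Step 1. What each definition counts**

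| Event | Protocol M.2 / SAP 3.2 | SAP 10.2 |
|---|---|---|
| Non-surgical treatment for a pelvic floor disorder, either arm | Yes | No |
| Office uterine or cervical procedure, hysteropexy arm, not for a surgical complication | Yes | No |
| Operating-room uterine or cervical procedure, hysteropexy arm | Yes | Yes |
| Operating-room reoperation for another gynecologic or pelvic condition that is not a pelvic floor disorder, either arm | No | Yes |
| Office procedure for a surgical complication that is not a pelvic floor disorder, either arm | No, unless uterine or cervical in the hysteropexy group | Yes |

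The closing list in 10.2 (recurrent prolapse, stress incontinence, other gynecologic conditions) follows the reoperation clause. It widens the operating-room limb and not the office limb. So 10.2 is narrower in the first two rows and wider in the last two.

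**Step 2. Is the difference explained?** The vaginal bleeding and dyspareunia rows of the same table say that their definitions changed at masked review. This row carries no such note, and section 14 is blank.

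**Step 3. Direction of the two omissions**

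Inputs:
- u: share of the hysteropexy arm whose only qualifying event is an office uterine or cervical procedure unrelated to a surgical complication. Assumed 1% to 10%.
- s: share of treatment failures whose only qualifying event is non-surgical treatment, taken as equal in both arms. Assumed 0 to 1.
- Two-year failure rates from the design assumptions in Protocol section N: native tissue 1 − 0.80 = 0.20; mesh 1 − 0.91 = 0.09.

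The first omission lowers the native-tissue rate by 0.20s and the mesh rate by 0.09s. The second lowers the mesh rate by u.

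Net shift toward mesh = u − s × (0.20 − 0.09) = u − 0.11s.

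Example: u = 0.03 and s = 0.25 give 0.03 − 0.0275 = 0.0025, or +0.25 points.

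| u | s = 0 | s = 0.25 | s = 0.50 | s = 1 | Break-even s = u/0.11 |
|---|---|---|---|---|---|
| 1% | +1.00 | −1.75 | −4.50 | −10.00 | 0.09 |
| 3% | +3.00 | +0.25 | −2.50 | −8.00 | 0.27 |
| 5% | +5.00 | +2.25 | −0.50 | −6.00 | 0.45 |
| 10% | +10.00 | +7.25 | +4.50 | −1.00 | 0.91 |

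Entries are percentage points; positive values favour mesh. With s = 0 the shift is u itself. The sign changes within plausible-looking inputs, and the documents fix neither u nor s. The illustration covers prolapse-related non-surgical treatment only. Treatment for incontinence or pain would add further unknown terms, as would the events that 10.2 adds.

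For scale, the SAP table shells show 88 hysteropexy and 87 hysterectomy participants, so one woman is 1/88 = 1.14 or 1/87 = 1.15 points.

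**The case against.** The strongest reply is that little is hidden. Operating-room uterine and cervical procedures remain in the variable. Uterine or cervical pathology and vaginal bleeding are separate compared outcomes. Mesh complications are graded by intervention, including office intervention, and all adverse events are summarised by arm. Pessary use counts as failure in the primary outcome and enters the cost analysis. SAP 7.7 makes safety p-values descriptive. All of this stands and limits the damage. None of it restores the planned count: the pathology row is coded from adverse event terms and does not count procedures, and the primary outcome does not cover non-surgical treatment for incontinence or pelvic pain.

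A reader might infer more: that 10.2 tilts the whole comparison toward mesh, by something like 3 to 10 points. The documents do not support that. Non-surgical treatment is lost from both arms, and at the design failure rates more of it could be lost from native tissue, which works against mesh. The 3% to 10% is an assumed rate with no source in the documents. Eligibility points to the low end, since it requires 12 months of amenorrhea and no cervical screening need for at least 3 years, and excludes uterine abnormalities and raised dysplasia risk. The variable is also binary, so a woman with another qualifying event is still coded Yes. Nor do the documents suggest that the definition was chosen to favour an arm.

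Finally, 10.2 may simply mirror what the visit forms ask. The forms are not in the documents, so this cannot be checked. If so, the limitation needs stating.

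**Conclusion.** The inconsistency is real and should be corrected. As written, SAP 10.2 would report a named Secondary Aim 2 safety outcome under a definition that differs from Protocol M.2 and from SAP 3.2, with no recorded reason. This rests on the text alone.

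The only directional statement that holds is limited. By the protocol's own wording ("Any subsequent uterine or cervical office or Operating Room procedure in hysteropexy group"), the omitted office uterine and cervical procedures belong to one arm, so that omission by itself can only lower the hysteropexy count. Net direction and size across both omissions are undetermined; the range of −10 to +10 points rests on assumed values of u and s together with the design failure rates. The effect is on the reported safety counts and percentages. The formal test of the primary hypothesis is untouched.

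**What to change.** Align the SAP 10.2 definition with SAP 3.2 viii and Protocol M.2 item 4. Report by arm, separately and combined:

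1. treatment for pelvic floor disorders, split into surgical and non-surgical, whether or not prompted by a surgical complication;
2. uterine or cervical procedures, split into office and operating room.

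Draw on the visit forms, the adverse event log and the resource-use data planned for the cost analysis (SAP 9.4.5). Separate reporting shows how much of each arm's total comes from the retained uterus and how much from pelvic floor treatment. If the wider operating-room and complication-related events in 10.2 are wanted, keep them as an additional, separately labelled variable.

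If the 10.2 wording was deliberate, record the change and its reason in SAP section 14. If the forms capture only complication-driven office procedures, state that limitation beside the result.

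The cost is a wording change and some reprogramming. The remaining risk is incomplete capture of office procedures, which cannot be judged without the forms.

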10.3 Deaths and Serious Adverse Events

A serious adverse event (SAE) is defined as any event that occurs during the 'active' phase of treatment, or the follow-up periods, and either: (1) results in death, or (2) requires inpatient hospitalization or a prolongation of existing hospitalization, or (3) is a congenital anomaly/birth defect, or (4) results in persistent or significant disability / incapacity, or (5) is life-threatening, or (6) requires intervention to prevent one of the above outcomes.

SAEs will be listed and SAEs, treatment-related SAEs and SAEs with an outcome of death will be summarized by treatment arm and site if there are enough events to summarize. Separate displays listing and summarizing death will also be created.

10.4 Other Safety Outcomes

All AEs identified on the AE forms will be summarized by treatment arm using MedDRA-classified verbatim terms and system organ class with numbers and percentages summarized by treatment arm.

10.5 Concomitant Medications

Limited data on concomitant medications related to pelvic floor disorders as well as antibiotic information will be collected as a part of this protocol. These medications will be listed and the number of subjects receiving each medication will be summarized by each reported term as well as drug class separately for each treatment. No formal analysis of concomitant medications is planned.

11 PHARMACOKINETIC ANALYSES

No pharmacokinetic analyses are planned.

12 ANALYSIS OF OTHER OUTCOMES

No analyses of outcomes other than efficacy and safety/tolerability outcomes are planned.

13 REPORTING CONVENTIONS

Unless required otherwise by a journal, the following rules are standard:

- Moment statistics including mean and standard deviation will be reported at 1 more significant digit than the precision of the data.
- Order statistics including median, min and max will be reported to the same level of precision as the original observations. If any values are calculated out to have more significant digits, then the value should be rounded so that it is the same level of precision as the original data.
- Following SAS rules, the median will be reported as the average of the two middle numbers if the dataset contains even numbers.
- Test statistics including t and z test statistics will be reported to two decimal places.
- P-value will be reported to 3 decimal places if > 0.001. If it is less than 0.001 then report '<0.001'. Report p-values as 0.05 rather than .05.
- No preliminary rounding should be performed, rounding should only occur after analysis. To round, consider digit to right of last significant digit: if < 5 round down, if >=5 round up.

14 CHANGES TO THE ANALYSES PLANNED IN THE PROTOCOL

To be completed at a later date

16 LIST OF POTENTIAL DISPLAYS

Data displays may be added, deleted, rearranged or the structure may be modified after finalization of the SAP. Such changes require no amendment to the SAP as long as the change does not contradict the text of the SAP. Also note that specific display shells will be generated for each potential manuscript and reviewed by the protocol team prior to the initiation of analyses for that manuscript.

Tables
Participant Eligibility
Participant Disposition
Protocol Deviations
Demographic and Baseline Characteristics
Primary Efficacy Model Results
Secondary Efficacy Outcome Measures
Safety and Tolerability Summary
Adverse Events

Figures

Consort diagram of participant disposition

Duration of Treatment Success Kaplan Meier Curves

Data Listings

Subject Eligibility

Subject Disposition

Protocol Deviations

Adverse Events

Serious Adverse Events

